| EFFICACY EVALUATIONS | 
Primary outcome measures:
 
 1. Safety: Heart rate (HR), blood pressure (BP), respiration (pulse oximetry, end tidal CO₂ (EtCO₂), respiratory rate), agitation and sedation (Richmond Agitation Sedation Scale). 2. Buprenorphine PK: Plasma concentration-time profiles of buprenorphine and its metabolite norbuprenorphine 3. Lemborexant PK: Plasma concentration-time profiles of lemborexant and its major metabolite M10. 
Adverse event data will be compiled for lemborexant and placebo cohorts and presented as summary statistics.
 
Secondary Outcome Measures:
 
 1. Subjective effects on opioid craving, anxiety and lemborexant drug liking as measured by a visual analog scale (VAS), and Brief Substance craving scale (BSCS), and opioid withdrawal based on the Subjective Opioid Withdrawal Scale (SOWS). 2. Objective opioid withdrawal based on the Clinical Opioid Withdrawal Scale (COWS). 3. Impulsivity as measured by a delayed discounting task (DDT). |

| | |
|---|--|
| | 
Exploratory Outcome Measures:
 
 1. Change in pupil size, as measured by single pupil measurements at scheduled times, using a pupillometer. 2. Behavioral/clinical profiles correlated with treatment response generated from PhAB application. 3. Change in sleep, as measured by self-reported sleep measures Pittsburgh Sleep Quality Index and Sleep Diary. |
| PLANNED INTERIM ANALYSES | 
There will be no formal interim analysis.
 |

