| STATISTICS Primary Analysis Plan | 
Initial analyses will evaluate group differences on demographic and baseline variables, will use contingency tables with chi-square testing, ANOVA's, and examination of correlations between baseline variables, subjective responses, and clinical results. General data analysis procedures: Prior to data analysis procedures, groups will be examined for differences in baseline characteristics that could potentially influence treatment outcome. Any variables that differ between groups and are related to outcome measures will be examined as potential covariates in subsequent data analyses.
 
Primary outcome measures:
 
 1. Safety: Heart rate (HR), blood pressure (BP), respiratory rate, agitation and sedation (Richmond Agitation-Sedation Scale) and pulse oximetry during a placebo dose will be compared to HR and BP during each lemborexant dose (5 mg and 10mg doses). Changes in safety measures induced by lemborexant dose along with buprenorphine will be compared to those without lemborexant, by lemborexant dose level (5 mg and 10 mg doses), using a generalized linear mixed model analysis with the participant as a random effect for each outcome. Adverse event data will be compiled for lemborexant and placebo cohorts and presented as summary statistics. 2. Buprenorphine PK: Plasma concentration-time profiles of buprenorphine and its metabolite norbuprenorphine after doses during the lemborexant placebo/administration (Day 0,1, 2) will be analyzed to obtain pharmacokinetic parameter estimates of buprenorphine (Cmax, Tmax, AUC, apparent t½, CL/F for parent buprenorphine and metabolic (AUC) ratios for metabolites) by individual. These parameters will be compared within subjects on sessions with lemborexant. 3. Changes in secondary outcome and exploratory outcome measures induced by lemborexant dose along with buprenorphine will be compared to those without lemborexant, by lemborexant dose level (5 mg and 10 mg doses), using a generalized linear mixed model analysis with the participant as a random effect for each outcome. |

| | |
|----------------------------------|---|
| RATIONALE FOR NUMBER OF SUBJECTS | Projected sample size is 18 subjects who have completed at least one drug-drug interaction treatment session with primary endpoint data— 12 lemborexant-treated subjects, 6 placebo treated subjects. Sample size was determined based on primary outcome safety and PK measures. |

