Exploratory aim: To determine the effect of lemborexant on central mu receptor function as measured by pupliometry and self-reported sleep measures, and to assess whether behavioral profiles based on a previous factor analysis of a phenotypic database predict behavioral response to lemborexant when added to buprenorphine-naloxone.

STUDY RATIONALE AND HUMAN SUBJECTS PROTECTION

The overall goal of this project is to develop initial human data on effects of novel compounds on safety (interactions with buprenorphine-naloxone) and efficacy (subjective response to lemborexant) in opioid use disorder subjects currently in treatment with buprenorphine-naloxone. The compound to be studied will be lemborexant.

Risk / Benefit Assessment

Potential risks are listed below. The primary risks to participate in this study are those involved from potential unexpected serious adverse events due to receiving lemborexant and buprenorphine. The risks of the medications are provided below. In order to reduce risks associated with exposure to COVID-19, study staff will follow VCU policy regarding COVID-19 safety procedures (e.g., wearing face masks, maintaining social distancing requirements, use of hand sanitizer, etc). Study activities that can be conducted remotely will be completed via zoom and/or phone call (e.g., portions of the screening and/or follow-up visits). Additionally, participants will be tested for COVID-19 prior to each CRU admission based on VCUHS guidance. Outpatient study visits will be scheduled to occur at the time of the patient clinic appointment whenever possible. Finally, in-person research interactions will be reduced to the minimum amount of time needed to complete study procedures and insure participant safety.

Risks of Lemborexant Administration

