Study Hypotheses: 1. *Adjunctive lemborexant (compared to placebo) will not alter the PK of buprenorphine-naloxone significantly, nor will it alter the pharmacodynamic properties related to safety (e.g., ECG, pulse oximetry changes, capnography, significant increases in sedation and agitation).* **Secondary hypotheses:** 2. *Adjunctive lemborexant will reduce subjective opioid craving, anxiety, opioid withdrawal, and impulsivity).* **Exploratory hypotheses:** 3. *Adjunctive lemborexant will not affect central mu opioid receptors as measured by pupillometry, but will increase subjective sleep ratings and behavioral effects of lemborexant will be related to behavioral profile measures from the NIDA phenotyping battery.*

Brief description of the protocol: The overall goal of this project is to develop initial human data for lemborexant combined with buprenorphine-naloxone on safety (e.g., interactive effects on cardiovascular and respiratory function, and agitation and sedation) and efficacy (subjective craving and anxiety, opioid withdrawal and impulsivity) in opioid use disorder participants. The sample will be recruited from VCU MOTIVATE clinic and other treatment programs and consist of participants with opioid use disorder of at least moderate severity that have been stabilized on buprenorphine-naloxone sublingual film daily dose ranging from 8mg/2mg to 24mg/6mg or buprenorphine sublingual tablet dose ranging from 5.7mg/1.4mg to 17.1/4.3 once daily.

PRIMARY Endpoints:

1. Safety: Heart rate (HR), blood pressure (BP), respiration (pulse oximetry, end tidal CO₂ (EtCO₂), respiratory rate), agitation and sedation (Richmond Agitation Sedation Scale).
2. Buprenorphine PK: Plasma concentration-time profiles of buprenorphine and its metabolite norbuprenorphine
3. Lemborexant PK: Plasma concentration-time profiles of lemborexant and its major metabolite M10.

SECONDARY Endpoints:

1. Subjective effects on opioid craving, anxiety and lemborexant drug liking as measured by a visual analog scale (VAS), and Brief Substance craving scale (BSCS), and opioid withdrawal based on the Subjective Opioid Withdrawal Scale (SOWS).
2. Objective opioid withdrawal based on the Clinical Opioid Withdrawal Scale (COWS).
3. Impulsivity as measured by a delayed discounting task (DDT).

EXPLORATORY Endpoints:

1. Change in pupil size as an indicator of central nervous system mu-opioid pharmacological effects (Rollins, Feiner et al. 2014, measured by pupillometry.).

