1. Subjective effects on opioid craving and anxiety as measured by a visual analog scale, and brief substance craving scale, and opioid withdrawal based on the Subjective Opioid Withdrawal Scale.
2. Objective opioid withdrawal based on the Clinical Opioid Withdrawal Scale.
3. Impulsivity as measured by delayed discounting. All measures will be compared between subjects receiving lemborexant versus those on placebo to determine the extent to which this measure is modified by the administration of lemborexant with buprenorphine vs. placebo with buprenorphine.

Exploratory Outcome Measures:

1. Pupillometry is used to measure change in pupil size as an indicator of lemborexant changes in buprenorphine central nervous system mu-opioid pharmacological effects (Rollins, Feiner et al. 2014). Single pupil measurements at scheduled times will be performed using a pupillometer per manufacturer's specification. The light in the measurement room will be maintained at 3.6 to 4.3 lux, using a Lutron light meter. Participants will be allowed to adjust to the room lighting for at least 3 minutes prior to any measurement. Pupillometry will be measured using the right eye for all participants, unless otherwise determined by the Investigator. The same eye will be used for all measurements in the study.
2. Sleep quality as measured by sleep diary and Pittsburgh Sleep Quality Index.
3. Relationship between baseline behavioral profiles as determined by the NIDA Phenotyping Battery and subjective response to lemborexant.

STUDY DRUG AND DOSAGE

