A protocol violation occurs when the investigator fails to adhere to significant protocol requirements affecting the inclusion, exclusion, subject safety and primary endpoint criteria except when performed for participant safety. Protocol violations for this study include, but are not limited to, the following:

Failure to meet inclusion/exclusion criteria

Failure to comply with Good Clinical Practice (GCP) guidelines will also result in a protocol violation. The investigator will determine if a protocol violation will result in withdrawal of a subject.

When a protocol violation occurs, it will be discussed with the investigator and a Protocol Violation Form detailing the violation will be generated. A copy of the form will be filed in the site's regulatory binder, and these will be reported to VCU IRB and the DSMB.

DATA SAFETY MONITORING

The Data Safety and Monitoring Plan includes establishment of a Data Safety Monitoring Board who will include five individuals who are completely independent of the investigators and who have no financial, scientific, or other conflict of interest with the trial. Each member will provide written documentation attesting to absence of conflict of interest. Additionally, [name] will serve as the on site medical monitor for the study.

For full data safety monitoring information see the Data Safety Monitoring Plan.

STATISTICAL METHODS AND CONSIDERATIONS

Initial analyses will evaluate group differences on demographic and baseline variables, will use contingency tables with chi-square testing, ANOVA's, and examination of correlations between baseline variables subjective responses and clinical results. General data analysis procedures: Prior to data analysis procedures, groups will be examined for differences in baseline characteristics that could potentially influence treatment outcome. Any variables that differ between groups and are related to outcome measures will be examined as potential covariates in subsequent data analyses.

Primary outcome measures:

1. Safety: Heart rate (HR), blood pressure (BP), respiratory rate, agitation and sedation (Richmond Agitation-Sedation Scale) and pulse oximetry during a placebo dose will be compared to HR and BP after each lemborexant dose (5 mg and 10 mg doses). Changes in safety measures induced by lemborexant dose along with buprenorphine will be compared to those without lemborexant, by lemborexant dose level (5 mg and 10

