mg doses), using a generalized linear mixed model analysis with the participant as a random effect for each outcome. Adverse event data will be compiled for lemborexant and placebo cohorts and presented as summary statistics.

2. Buprenorphine PK: Plasma concentration-time profiles of buprenorphine and its metabolite norbuprenorphine after doses during the lemborexant placebo/administration (Day 0, 1, 2) will be analyzed to obtain pharmacokinetic parameter estimates of buprenorphine (Cmax, Tmax, AUC, apparent t_{1/2}, CL/F for parent buprenorphine and metabolic (AUC) ratios for metabolites) by individual. These parameters will be compared within subjects on sessions with lemborexant. Lemborexant PK will be compared with published lemborexant PK data. As it would be unethical to withhold buprenorphine treatment from patients who are on buprenorphine for MAT, there will be no lemborexant dose without buprenorphine.

3. Changes in secondary outcome measures induced by lemborexant dose along with buprenorphine will be compared to those without lemborexant, by lemborexant dose level (5 mg and 10 mg doses), using a generalized linear mixed model analysis with the participant as a random effect for each outcome.

Safety and tolerability data will be summarized by treatment group.

Adverse event rates will be coded by body system and MedDra classification term. Adverse events will be tabulated by treatment group and will include the number of patients for whom the event occurred, the rate of occurrence, and the severity and relationship to study drug.

Interim Analysis

There will be no formal interim analysis.

Rationale for sample size: Sample size for effect of lemborexant on recommendations from the FDA regarding phase I safety studies.

DATA COLLECTION, RETENTION AND MONITORING

Data Collection Instruments

The Investigator will prepare and maintain adequate and accurate source documents designed to record all observations and other pertinent data for each subject treated with the study drug.

Study personnel at each site will enter data from source documents corresponding to a subject's visit into the protocol-specific paper/electronic CRF when the information corresponding to that visit is available. Subjects will not be identified by name in the study database or on any study documents to be collected by the Sponsor (or designee), but will be identified by a subject number.

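### The exploratory question of which baseline profiles predict response to lemborexant is given only a correlation, with response undefined and no profile-by-treatment contrast

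*Combined protocol and SAP*

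**What the plan says.** The profile question appears in several places, always as a question about the drug:

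- Specific Aims, Exploratory aim: whether profiles from an earlier factor analysis "predict behavioral response to lemborexant when added to buprenorphine-naloxone".
- Study Hypotheses, exploratory: "behavioral effects of lemborexant will be related to behavioral profile measures from the NIDA phenotyping battery".
- Synopsis, Exploratory Outcome Measures 2, and again under Exploratory Endpoints: "Behavioral/clinical profiles correlated with treatment response generated from PhAB application".
- Study Outcome Measures, Exploratory Outcome Measures 3: "Relationship between baseline behavioral profiles as determined by the NIDA Phenotyping Battery and subjective response to lemborexant".

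Correlation is the only method attached to it. For the secondary measures listed just above in Study Outcome Measures, the plan does name the control: "All measures will be compared between subjects receiving lemborexant versus those on placebo". The profile outcome has no matching sentence.

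The two statistical texts differ. The Synopsis (Statistics, item 3) reads "Changes in secondary outcome and exploratory outcome measures induced by lemborexant dose along with buprenorphine will be compared to those without lemborexant", by dose, in a mixed model with a random participant effect. The same item in Statistical Methods and Considerations reads "Changes in secondary outcome measures induced by lemborexant dose along with buprenorphine will be compared to those without lemborexant", with exploratory outcomes left out. Neither contains a profile term.

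**The concern.** A trait can be associated with ratings under lemborexant for two reasons. It may be prognostic, meaning that people with the trait rate higher or lower whatever they are given. Or it may modify the drug effect, so that the lemborexant-placebo difference varies with the trait. Only the second is prediction of response to lemborexant, and a correlation between profile and rating mixes the two.

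Prognostic association is likely here because the screening instruments overlap with the outcomes. The Brief Substance Craving Scale is both a platform instrument and a secondary outcome. An adjusting delay-discounting task is in the battery, and delay discounting is the impulsivity outcome. The battery contains an anxiety scale, and anxiety is rated on a VAS.

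At stake is one exploratory conclusion. It could travel, however: the Background ties this phenotyping work to precision medicine, so an apparent responder profile might steer a later trial. The data for the right contrast are already being collected, since Table 2 schedules the same screening battery and the same Day 0 and Day 2 ratings for all participants.

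**Working it through.** **Inputs from the documents.** There are 12 lemborexant and 6 placebo completers, allocated 2:1 (Synopsis; Dosage/Dosage Regimen): 12 + 6 = 18. The plan gives no alpha, power or effect size for the profile question, so it has no figure to reproduce.

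**Assumptions.** Two-sided 5% level; one standardised normal trait; one rating per person; trait-rating correlation r = 0.3, 0.5 or 0.7; 40,000 simulated trials per scenario.

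**Step 1: threshold for a correlation.** Critical |r| = t/√(n − 2 + t²).
- n = 12: 2.228/√(10 + 4.964) = 0.576.
- n = 18: 2.120/√(16 + 4.494) = 0.468.

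**Step 2: purely prognostic trait, response taken as the raw on-drug rating.** The slope is the same in both arms, so there is no effect modification to find. The interaction test is t = (b_L − b_P)/√{s²(1/Sxx_L + 1/Sxx_P)} on 12 + 6 − 4 = 14 df, where b_L and b_P are the slopes in the lemborexant and placebo arms. The share of trials flagging the trait is:

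| Analysis | r = 0.3 | r = 0.5 | r = 0.7 |
|---|---|---|---|
| Correlation, lemborexant arm only | 16% | 40% | 78% |
| Both arms pooled, arm-adjusted, no interaction | 22% | 56% | 92% |
| Profile-by-treatment interaction | 5% | 5% | 5% |

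Adding the placebo participants without an interaction makes the false flag more frequent. The missing element is the contrast between arms.

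**Step 3: the same trait, response taken as change from Day 0.** If the trait shifts the Day 0 and dosing-day ratings equally, then change = (r·trait + e₂) − (r·trait + e₀) = e₂ − e₀, and the trait drops out. In simulation the lemborexant-only correlation flags about 5% at every r. What does not drop out is any trait-related drift between Day 0 and the dosing day, such as expectancy or familiarity with the sessions. That drift is also present on placebo, and only the placebo arm can remove it.

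**Step 4: what the interaction can deliver.** If the slope exists only under lemborexant, power is about 8%, 16% and 31% at r = 0.3, 0.5 and 0.7. The last figure rises to about 35% if the residual SD, rather than the total SD, is taken as equal in the two arms. For precision, take Sxx ≈ 11 and 5, t₁₄ = 2.145 and, at r = 0.5, s = √(1 − 0.25) = 0.866. The half-width of the 95% interval is then about 2.145 × 0.866 × √(1/11 + 1/5) = 1.0 SD of rating per SD of trait. The simulated median half-widths run from about 0.9 to 1.2, larger than any slope difference assumed here.

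**The case against.** Three stronger readings are tempting, and the documents do not support them.

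- *The placebo arm is left out.* A reader might infer this from the phrase about response to lemborexant, but nothing excludes placebo participants. The term treatment response could cover both arms, and the Synopsis nominally compares exploratory outcomes with those without lemborexant.
- *The plan will report prognostic traits as predictors of drug response.* No text says how the result will be reported. This is a risk of the method, not a stated intention.
- *The mixed model cannot be used because the battery is given only at screening.* The repeated outcome would be the ratings, and a screening profile can enter as an ordinary baseline covariate. The plan already allows baseline covariates.

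Nor does the opening of Statistical Methods and Considerations, with its "examination of correlations between baseline variables subjective responses and clinical results", settle the matter. It describes preliminary work across groups and is not tied to the profile aim.

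The strongest objection concerns size. The plan speaks of response, effects and induced changes, and Table 2 schedules the relevant ratings on Day 0, when buprenorphine is given without lemborexant. If response means change from Day 0, the 40% at r = 0.5 falls to about 5% for a trait that affects level alone. This stands: the large figures hold only for raw on-drug ratings. But the documents do not choose between the definitions, and under change scores trait-related expectancy or time effects remain. It is also fair that the interaction has little power, and that no primary or secondary conclusion depends on this outcome.

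**Conclusion.** The concern holds in a limited form. The profile question is about modification of a drug effect, the only method named for it is a correlation, response is undefined, and no profile-by-treatment contrast is specified. Neither a lemborexant-only nor a pooled correlation can answer it.

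The size depends on the missing definition. For a purely prognostic trait, the lemborexant-only false-flag rate is about 16% to 78% with raw on-drug ratings over assumed r = 0.3 to 0.7. It is about 5% with change from Day 0 when the trait affects level alone, and is not quantified where trait-related expectancy or time effects exist. All these figures assume a two-sided 5% test that the plan does not state.

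Severity is minor: the outcome is exploratory, in an 18-person study whose size was set on safety and PK.

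**What to change.** 1. In Synopsis Exploratory Outcome Measures 2, Exploratory Endpoints 2 and Study Outcome Measures Exploratory 3, define response as the dosing-day rating adjusted for its Day 0 value, at both the Week 1 Day 2 and Week 2 Day 2 sessions.
2. In the Synopsis statistics item 3 and in Statistical Methods and Considerations item 3, add a profile-by-treatment term (lemborexant versus placebo) to the mixed model with participant as random effect. Limit it to the factor scores from the earlier factor analysis named in the Exploratory aim.
3. Report the difference in slopes with a 95% interval, labelled hypothesis-generating. Describe any within-arm correlation as an association, not as a predictor of drug response.
4. Reconcile the two item 3 texts on whether exploratory outcomes are in the mixed model.

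The cost is wording only; no new data are needed. The downside should be stated in the plan: with six placebo participants the interval will be wide and power low (about 8% to 35% under the assumed effects), so the analysis supports estimation and not a claim that a responder profile has been found or ruled out.

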On PK/Safety Testing week 1 Study Day 2 lemborexant (or matching placebo) is given as 5 mg at 7:00 AM after an overnight stay on the CRU. On PK/Safety Testing Week 2 Study Day lemborexant (or matching placebo) is given as 10 mg at 7:00 AM. Subjects will be continuously monitored on the CRU for 8 hours after the lemborexant dose, which is past the C_{max} lemborexant concentration, which will occur between 8:00 AM and 10:00 AM. Blood samples for determination of buprenorphine concentration and its major metabolite norbuprenorphine and lemborexant and its major metabolite M10 will be collected pre-dose and specified timepoints during the hospital stay (Table 3). Plasma levels will be utilized to determine AUC (area under the concentration–time curve from Time 0 post-dose to infinity) and $T_{1/2}$ (apparent terminal half-life) using noncompartmental analysis, and C_{max} (maximum concentration), C_{24} (concentration at 24 hours post-dose), and T_{max} (time to C_{max}). Plasma buprenorphine and norbuprenorphine and lemborexant and M10 levels will be determined in the VCU Department of Pharmacology and Toxicology drug analysis laboratory.

Dispensing: Study drug will be dispensed by the research pharmacist and administered by the research nurse on the CRU.

Supply of Study Drug at the Site: Study drug will be provided to the CRU after an order from the study physician or nurse practitioner. Storage: At the testing facility, all lemborexant, buprenorphine, and placebo must be kept in a secure, locked storage place with access limited to authorized study personnel only.

Study Drug Accountability: All study medication will be administered on the CRU. The study staff will record an accurate accounting of each medication administered.

STUDY PROCEDURES AND GUIDELINES

A Schedule of Events representing the required testing procedures to be performed for the duration of the study is diagrammed in Tables 1-2. Prior to conducting any study-related activities, written informed consent and the Health Insurance Portability and Accountability Act (HIPAA) authorization must be signed and dated by the subject. In order to better accommodate participant schedules, PK/Safety Testing Weeks 1 and 2 may be separated by up to approximately 14 days.

Clinical Assessments:**Concomitant Medications**

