Pregnancy Test

A urine pregnancy test will be obtained from female subjects who are of childbearing age prior to their participation in the study.

Urinalysis

Urine will be obtained and sent to the clinical laboratory for determination of color, specific gravity, pH, protein, glucose, ketones, and blood.

Urine Drug Screen

Urine will be obtained from all subjects to be tested for cocaine (benzoylecgonine), opiates and opioids, benzodiazepines, fentanyl, amphetamine, methamphetamine, and THC.

Breathalyzer or salivary alcohol level

Breath or salivary alcohol level will be obtained from all subjects. Subjects who have a positive breath or salivary alcohol will be told that they must return at a later date with a negative alcohol test in order to take part in study procedures.

Pharmacokinetic Measurements

Pharmacokinetic samples for analysis of buprenorphine and its metabolites: Blood samples for analysis of the pharmacokinetics of buprenorphine-naloxone dose and lemborexant 5 and 10mg will be collected at baseline on day 0, and on PK/Safety Testing week 1, day 2, PK/Safety Testing week 2, day 2. After separation of plasma by routine methods, samples will be frozen at -70°C until ready for analysis. Plasma concentrations of buprenorphine and metabolite (norbuprenorphine) and lemborexant and metabolite (M10) will be assayed by liquid chromatography-tandem mass spectrometry.

Pupilometry measurement

Pupilometry is used to measure change in pupil size as an indicator of central nervous system mu-opioid pharmacological effects (Rollins, Feiner et al. 2014). Change in pupil size, as measured by single pupil

| Table 3. Schedule for blood samples for PK testing | | |
|--|---|---|
| Day 0 Baseline Buprenorphine PK | PK/Safety Week 1, Day 2 (and similarly Week 2, Day 2) | PK/Safety Week 1, Day 3 (and similarly Week 2, Day 3) |
| | 7:00 am (Pre-lemborexant dose at 7:05) | 7:00 am (if still on inpatient unit) |
| | 7:30 | |
| 8:00 am (Pre-buprenorphine dose at 8:05) | 8:00 am (Pre-buprenorphine dose at 8:05) | 8:00 am (pre-buprenorphine dose at 8:05) |
| 8:15 | 8:15 | |
| 8:30 | 8:30 | |
| 8:45 | 8:45 | |
| 9:15 | 9:15 | |
| 9:30 | 9:30 | |
| 10:00 | 10:00 | |
| 10:30 | 10:30 | |
| 11:00 | 11:00 | |
| 11:30 | 11:30 | |
| 12:00 | 12:00 | |
| 2:00 | 2:00 | |
| 4:00 | 4:00 | |

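### The only AUC defined for buprenorphine runs to infinity, which would not yield clearance (CL/F) under daily maintenance, and Day 0 and the lemborexant sessions may rest on unequal sampling windows

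*Combined protocol and SAP*

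**What the plan says.** Study Drug and Dosage says that samples for buprenorphine, norbuprenorphine, lemborexant and M10 are taken at the Table 3 times. It then states: "Plasma levels will be utilized to determine AUC (area under the concentration–time curve from Time 0 post-dose to infinity". Half-life comes from the same noncompartmental analysis, and a 24-hour concentration is also listed. No other AUC interval appears in the document.

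Primary outcome 2 (synopsis, Study Outcome Measures, Statistical Methods and Considerations) lists buprenorphine Cmax, Tmax, AUC, apparent half-life and "CL/F for parent buprenorphine and metabolic (AUC) ratios for metabolites", with no interval and no formula. Statistical Methods adds: "These parameters will be compared within subjects on sessions with lemborexant". No reference day is named. The hypothesis is framed against placebo: "Adjunctive lemborexant (compared to placebo) will not alter the PK of buprenorphine-naloxone significantly".

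The protocol description says participants are those "that have been stabilized on buprenorphine-naloxone sublingual film daily dose ranging from 8mg/2mg to 24mg/6mg", or the tablet equivalent, once daily. They receive their usual dose on profile days.

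Table 3 (blood samples) times the buprenorphine dose on Day 0 and on Day 2 of each week the same way, "8:00 am (Pre-buprenorphine dose at 8:05", and the last same-day sample on each is at 4:00 pm. Only the sessions have a Day 3 column, with an 8:00 am sample before the next buprenorphine dose.

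**The concern.** Two separate problems arise.

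First, an AUC to infinity suits a single dose in a drug-free subject. Under once-daily maintenance the concentrations after a dose also contain the tails of earlier doses. Dose divided by that AUC is therefore not clearance, and AUC ratios for norbuprenorphine inherit the same difficulty.

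Second, extrapolating to infinity depends on the terminal slope, and the slope depends on how late the last samples are. Day 0 is the active arm's only lemborexant-free profile. If the sessions have a next-morning sample and Day 0 does not, the two days estimate the slope over different stretches of the curve. A difference in AUC or half-life could then be read as a lemborexant effect, or could offset a real one. Buprenorphine PK is a primary outcome and the basis of the drug-interaction conclusion.

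**Working it through.** The plan gives no half-life, PK margin or PK variability, so there is no figure of its own to reproduce. Clock times come from Table 3; every pharmacokinetic value below is an assumption.

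**Sampling spans.** Day 0: 8:05 am to 4:00 pm is 7 h 55 min = 7.92 h. Sessions with the Day 3 sample: 8:05 am to 8:00 am next day is 23 h 55 min = 23.92 h.

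**CL/F.** At steady state, CL/F = dose/AUC(0–24). For single-phase decline, AUC(0–∞)/AUC(0–24) = 1/(1 − 2^(−24/t½)):

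| Assumed t½ | Ratio | Dose/AUC(0–∞) as share of true CL/F |
|---|---|---|
| 12 h | 1/(1 − 0.25) = 1.33 | 75% |
| 24 h | 1/(1 − 0.50) = 2.00 | 50% |
| 36 h | 1/(1 − 0.63) = 2.70 | 37% |

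With two-phase decline (set A below), the AUC to infinity estimated from the Day 0 samples is 0.87 to 1.31 times AUC(0–24). The CL/F error then runs from 1/0.87 − 1 = +15% to 1/1.31 − 1 = −24%, so even its sign is not fixed.

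**Matched windows.** If all three profiles end at 4:00 pm, an unchanged profile gives the same estimate each day. The no-interaction ratio is 1, although CL/F itself may be wrong.

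**Unmatched windows.** Error-free steady-state profiles, identical on both days, were sampled at the Table 3 times. AUC used the linear-up/log-down trapezoid. The terminal slope came from the last three points and, in set B, also from the best-fitting run of points. The Day 3 7:00 am sample, which is conditional on still being an inpatient, was left out.

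- Set A (terminal fraction 0.15–0.30 of the initial decline, first-phase half-life 1.5–3 h): session/Day 0 AUC(0–∞) ratio 1.18–1.38, 1.45–1.84 and 1.66–2.20 for terminal half-lives of 12, 24 and 36 h. Half-life ratio 1.5–3.2.
- Set B (terminal phase 30–70% of disposition area, first-phase half-life 2–4 h): AUC ratio 1.13–2.03 over the same half-lives.
- Set C (as set A, but with the fraction read as a share of area): AUC ratio 1.08–1.37.
- Single-phase decline: ratio 1.00 to within 1%.

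One case from set B: terminal half-life 24 h, first phase 2 h, half the area terminal. Estimated half-life is 3.5 h on Day 0 and 10.5 h in the session. AUC(0–∞) is 0.848 and 1.272 times AUC(0–24), so the ratio is 1.272/0.848 = 1.50 with no interaction.

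**Is the Day 3 sample drawn?** Table 3 lists the 8:00 am draw without condition, and the 24-hour concentration points the same way. Against this, the text of Pharmacokinetic Measurements says samples "will be collected at baseline on day 0, and on PK/Safety Testing week 1, day 2, PK/Safety Testing week 2, day 2", naming no Day 3. Study Drug and Dosage ties sampling to the hospital stay, and Table 2 allows discharge on Day 2. Table 3 also implies a Day 3 buprenorphine dose, whereas Table 2 marks buprenorphine only on Day 0 and Day 2.

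**After the fix.** AUC from dose to 4:00 pm uses identical samples, so the no-interaction ratio is exactly 1 for identical profiles. AUC(0–24), with the Day 0 pre-dose value standing in for the 24-hour value, gives 0.999–1.000.

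**The case against.** The strongest reply is that the definition may be meant for lemborexant. That section opens with lemborexant dosing, an AUC to infinity is natural for single lemborexant doses, and its parameter list differs from the buprenorphine list: CL/F is missing from the first and the 24-hour concentration from the second. A reader might infer that the reported CL/F will certainly be wrong. The documents do not support that, because no CL/F formula is given. What stands is that the definition follows directly on the naming of buprenorphine, and no other interval is offered.

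A reader might also infer that the interaction estimate is biased as planned. That goes too far. The artefact needs all three conditions. The within-subject comparison can be read as 5 mg against 10 mg, where the windows match. If no Day 3 sample is drawn, Day 0 matches too. A comparison of change from Day 0 between arms would cancel the artefact in expectation, but none is planned for PK. Day 0 nevertheless remains a plausible reference, since primary outcome 2 includes it among the profile days and Table 3 titles it the baseline profile.

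Finally, the ratios are ranges over chosen assumptions, not bounds, and the upward direction is a property of clean two-phase curves. That limit is accepted. Cmax and Tmax are unaffected by the window difference.

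**Conclusion.** The concern holds in a limited form. The only written AUC is of the wrong type for buprenorphine clearance under daily dosing. If CL/F is taken from it, CL/F is not clearance, but that error alone leaves a within-subject ratio unbiased when windows match. The window artefact is conditional on the Day 3 sample, Day 0 as reference and multi-phase decline. Its size, about 1.1 to 2.2 on AUC to infinity for assumed terminal half-lives of 12 to 36 h, is illustrative and falls to 1.00 with single-phase decline. If only some participants give the Day 3 sample, windows would also differ between participants. Because the parameter is primary and the remedy is mostly wording, it should be fixed; confidence is medium.

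**What to change.** For buprenorphine and norbuprenorphine, replace AUC to infinity as follows.

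- **Main comparison:** AUC from dose to 4:00 pm on Day 0, Week 1 Day 2 and Week 2 Day 2, with Day 0 named as the within-subject reference.
- **Supportive:** steady-state AUC(0–24), with CL/F = dose/AUC(0–24) for buprenorphine. Use the pre-dose value as the 24-hour value on Day 0, and the measured Day 3 value in the sessions where it exists.
- Do not compare terminal half-life across unequal windows.
- Record the clock time of the previous buprenorphine dose before each profile; Concomitant Medications captures only dates.
- Reconcile Table 3, the Pharmacokinetic Measurements text, Study Drug and Dosage and Table 2 on whether the Day 3 8:00 am sample is drawn for everyone, and reconcile Tables 2 and 3 on the Day 3 buprenorphine dose.

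AUC to infinity can stay for lemborexant.

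The cost is wording and one data field, plus some loss of information. AUC to 4:00 pm covers about 42–69% of the 24-hour AUC under set A, and it attenuates a true effect: a 20% fall in clearance shows as 1.03–1.11 against a true AUC(0–24) ratio of 1.06–1.19. Because 1/0.8 = 1.25 is not reached within one day, session CL/F would also understate such a change. AUC(0–24) depends on when the previous dose was taken. A previous dose 20 h or 28 h before Day 0 moves the no-interaction ratio to 0.92–0.95 or 1.04–1.08, and opposite shifts on the two days give 0.88–1.14. Carry-over affects the shorter AUC as well, which is why the clock time matters for both.
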